- The subject receives any of the disallowed concomitant medications.
- The subject is unwilling or unable to comply with the protocol.
- At the discretion of the Investigator for medical reasons or for noncompliance.

NOTE: Subjects who complete BG00012 treatment or permanently discontinue BG00012 for any of the aforementioned reasons and who have a lymphocyte count  $< \text{LLN}$  should not be withdrawn from the study. These subjects will be followed according to Section 11.3.

Efficacy Assessments:

Relapse assessment, EDSS, MRI analysis (on subjects who had MRI scans as part of Studies 109MS301 and 109MS302 and in 109MS303 up through and including Amendment 6), visual function as measured by low-contrast Sloan letter charts.

Health Economic Assessments:

SF-36, EQ-5D Quality of Life questionnaire.

Safety Assessments:

Physical examination, including vital signs, blood chemistry, hematology, urinalysis, urine cytology, and AE monitoring.

Statistical Analysis:

Efficacy:

ARR will be summarized for the extension study, as well as from the original baseline of the Phase 3 studies (i.e., extension study + 2 years in the previous Phase 3 studies).

A negative binomial regression model will be used for the

CONFIDENTIAL

The information contained herein may not be used, disclosed, or published without the written consent of  
Biogen MA Inc.

analysis of ARR. In addition to ARR, disability progression, proportion of subjects relapsed, visual function test scores, and MRI endpoints will also be analyzed. The Cox proportional hazards model will be used for the analysis of time to relapse/proportion relapsed and disability progression. Visual function test will be analyzed by an analysis of covariance (ANCOVA) model. For MRI endpoints, analyses will be conducted on all MRI data collected up through and including Amendment 6 of this protocol: the number of lesions will be analyzed by logit regression, and the volume of lesions, brain atrophy, and MTR will be analyzed by ANCOVA models.

Safety:

Safety data will be summarized for the extension study for all treatment groups. Long-term safety data (extension study + 2 years in the previous Phase 3 studies) will be summarized by treatment groups. In addition, analysis by 3- or 6-month intervals may also be performed. Lymphocyte count and lymphocyte subset data will be summarized by timepoints on BG00012 as well as post-treatment timepoints for subjects who permanently discontinue BG00012.

Health Economics:

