The duration of BG00012 administration in both studies was 96 weeks. Clinic visits occurred every 4 weeks, with the End of Study Visit at Week 96 for subjects who chose to enroll in this protocol and at Week 100 for subjects who chose not to enroll in this protocol. The safety profile of BG00012 was similar in Studies 109MS301 and 109MS302. Across both studies, the commonly reported AEs in the BG00012 BID group included flushing and hot flush, GI events (diarrhea, nausea, abdominal pain upper, abdominal pain, vomiting, and dyspepsia), skin events (pruritus, rash, and erythema), albumin urine present, aspartate transaminase (AST) increased, and lymphopenia.

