### 7.2.2. Treatment Period

Subjects will report to the study site every 4 weeks for the first 24 weeks (Visit 1 through Visit 6) and every 12 weeks thereafter.

Premature Study Treatment Withdrawal Visits and Unscheduled Relapse Assessment Visits will be performed as necessary. All efforts should be made to keep the subjects' visit schedule relative to their Baseline Visit (Day 1). Unscheduled Relapse Assessment Visits should not modify or replace their regular visit schedule.

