**14.3.1.2. Visit 1 (Week 4 ±5 Days)**

Treating Neurologist

- Monitoring of AEs

Treating Nurse

- Vital signs
- Collection of blood for blood chemistry
- Collection of urine for urine pregnancy test in women of childbearing potential; results must be known prior to BG00012 distribution
- Collection of urine for urinalysis. If urinalysis is abnormal, see Section 11.2.
- BG00012 distribution
- Recording concomitant medication and AEs

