### **14.3.2. Years 2 and 3 Treatment Visits**

#### **14.3.2.1. Visits 9, 10, 11, 13, 14, and 15 (Weeks 60, 72, 84, 108, 120, and 132 ±7 Days)**

#### Treating Neurologist

- Physical examination
- EDSS (may be performed by the *examining neurologist*)
- Monitoring of AEs

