### Section 4.3

**Change:** The frequency of some study procedures (clinical chemistry, hematology, urinalysis, physical examination, and urine pregnancy testing) was decreased from every 12 weeks to every 24 weeks during Year 4 through 8 of the treatment period. The study activities chart (Chart 2 of 2) was revised and new study activities charts for Years 2 and 3, Years 4 through 8, and post-treatment and unscheduled visits were created to reflect the new schedule of assessments as well as the extended duration of the study.

CONFIDENTIAL

The information contained herein may not be used, disclosed, or published without the written consent of Biogen Idec MA Inc.

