The incidence of AEs by SOC and PT may also be presented by time intervals (e.g., using a 12 month time interval). Other time intervals may be explored as well to elucidate trends over time. For such analyses, for a given time interval, the number of subjects who were followed for adverse events during that time interval will be presented along with the AE incidence during that time interval. Therefore, for a given SOC or PT, subjects will be counted only once for a given time interval but may be counted more than once across time intervals.

The incidence of AEs by relationship to study treatment will be summarized by SOC and PT. For a given SOC or PT, subjects with multiple AEs differing in relatedness will be counted once in the most related category. In addition, AEs categorized as "related" (i.e., those where the investigator assessment of relationship to study treatment is "possibly" or "related) will also be summarized by PT.

The incidence of AEs by severity will be summarized by SOC and PT using severity categories of mild, moderate, and severe. For a given SOC or PT, subjects with multiple AEs differing in severity will be counted once in the category of worst severity. The incidence of severe AEs will also be summarized by PT.

Deaths that occur will be described in detail in patient narratives. A listing of deaths will also be provided. While the number of deaths is expected to be small, tabulation will be performed if appropriate.

A summary of SAEs by SOC and PT will also be provided. Details of each SAE will also be listed, including subject ID, treatment group, system organ class/preferred term, date of onset, severity, and relationship to the study drug and action taken. In addition, a summary of treatment-related SAEs by SOC and PT will be provided.

The incidence of adverse events that led to study treatment discontinuation, study withdrawal, dose interruption, and dose reduction will each be presented by SOC and PT.

A listing of AEs leading to study treatment discontinuation and study withdrawal will also be presented. Adverse events that were treatment-emergent to the previous study yet led to study treatment discontinuation and study withdrawal in Study 109MS303 will be denoted by a negative onset day in the listing.

The incidence of adverse events of special interest will be summarized by SOC and PT. The adverse event of special interest categories may include the following:

- Flushing and other related symptoms;

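### If adverse events are tabulated by time interval, transient laboratory-detected hepatic and renal events are confounded with a testing schedule that falls from 8 to 4 to 2 tests per study year

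*SAP*

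**What the plan says.** **The interval analysis.** SAP 6.5.3 makes AE incidence by SOC and PT over time intervals an option and gives 12 months as an example. It continues: "Other time intervals may be explored as well to elucidate trends over time". For each interval it reports the number of subjects followed for AEs and the incidence among them. The protocol synopsis is also permissive and contemplates finer cuts: "analysis by 3- or 6-month intervals may also be performed".

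**What can count as an event.** Protocol 15.1.1 includes an abnormal laboratory finding among the things that may be an AE. Protocol 5.2 lists the commonly reported AEs in the BID group of the parent studies, among them "albumin urine present, aspartate transaminase (AST) increased, and lymphopenia". SAP 6.5.3 names hepatic and renal disorders as possible special-interest categories.

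**The testing schedule.** On visits, Protocol 7.2.2 says: "Subjects will report to the study site every 4 weeks for the first 24 weeks (Visit 1 through Visit 6) and every 12 weeks thereafter". Chemistry ("Collection of blood for blood chemistry") and urinalysis ("Collection of urine for urinalysis. If urinalysis is abnormal, see Section 11.2") are listed at every Year 1 visit and every visit in Years 2-3. In Years 4-8 they are listed at even-numbered visits only (Protocol 4.1 to 4.3 and 14.3.1 to 14.3.3). The amendment history dates the last reduction to Version 3: "clinical chemistry, hematology, urinalysis, physical examination, and urine pregnancy testing) was decreased from every 12 weeks to every 24 weeks". Hematology has since returned to at least 12-weekly (Protocol 4.5), so this point concerns chemistry and urinalysis only.

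Neither SAP 6.5.3 nor 6.5.4 mentions the change in testing frequency. The caution in SAP section 6 about later timepoints concerns the number of subjects, not the number of tests per subject.

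**The concern.** The primary objective is the long-term safety profile, and the interval table is the AE output aimed at time trends. A short-lived, symptomless rise in a liver enzyme or urine protein is recorded only if a sample is taken while it lasts. With the same risk throughout, fewer samples per year mean fewer such episodes recorded per year. The denominator, subjects followed, does not reflect this. A falling hepatic or renal row could then be read as risk declining with continued exposure when part or all of the fall comes from the schedule.

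The other planned laboratory outputs do not fill the gap. The by-visit summaries in SAP 6.5.4 give values and changes rather than rates of threshold abnormality over time. The shift and worst-value tables are not specified by interval.

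**Working it through.** The plan states no tests-per-year figure, so there is none to reproduce. The counts come from the schedules.

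**Step 1. Scheduled post-baseline chemistry and urinalysis per 48-week study year**

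- Year 1: Weeks 4, 8, 12, 16, 20, 24, 36, 48 = 8.
- Years 2-3: six visits ("Visits 9, 10, 11, 13, 14, and 15 (Weeks 60, 72, 84, 108, 120, and 132 ±7 Days") plus Visits 12 and 16 (Weeks 96 and 144) = 8 over 2 years = 4 per year.
- Years 4-8: Visits 18, 22, 26, 30, 34 and Visits 20, 24, 28, 32, 36 = 10 over 5 years = 2 per year.

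In true 12-month intervals the counts are 8, 4, 4, 2, 2, 3, 2, 1. The sixth interval holds Weeks 264, 288 and 312, and the last becomes 2 with the Week 388 End of Study Visit. In 12-week slices, the first holds three tests (Weeks 4, 8, 12), while in Years 4-8 every second slice holds none.

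**Step 2. Detection of a silent episode of fixed duration d, constant onset rate**

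An episode is caught if a scheduled test falls within it, so the probability is min(1, d/gap), averaged over the period. The gaps are:

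- Year 1: 4 weeks for 24 weeks, then 12 weeks for 24 weeks
- Years 2-3: 12 weeks
- Years 4-8: 24 weeks

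For d = 4:

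- Year 1: (24 × 1 + 24 × 4/12)/48 = 32/48 = 67%
- Years 2-3: 4/12 = 33%
- Years 4-8: 4/24 = 17%

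| Assumed duration | Year 1 | Years 2-3 | Years 4-8 |
|---|---|---|---|
| 4 weeks | 67% | 33% | 17% |
| 8 weeks | 83% | 67% | 33% |
| 12 weeks | 100% | 100% | 50% |
| 16 weeks | 100% | 100% | 67% |
| 24 weeks or more | 100% | 100% | 100% |

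The drop after Year 1 appears only for d below 12 weeks, and the drop at Year 4 only for d below 24 weeks. From Year 1 to Years 4-8 the ratio is 4 at 4 weeks, 2.5 at 8 weeks, 2 at 12 weeks and 1 at 24 weeks.

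**Step 3. A more extreme model: independent results at each test**

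With per-test probability p, the share with at least one abnormal result is 1 − (1 − p)^k, with k = 8, 4, 2.

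| Assumed p | Year 1 | Years 2-3 | Years 4-8 |
|---|---|---|---|
| 0.5% | 3.9% | 2.0% | 1.0% |
| 1% | 7.7% | 3.9% | 2.0% |
| 2% | 14.9% | 7.8% | 4.0% |
| 5% | 33.7% | 18.6% | 9.8% |

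The documents give neither d nor p; both are assumptions.

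**Step 4. Does restricting to common visits remove the artefact?**

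Every multiple of 24 weeks up to 384 carries both tests, giving 384/24 = 16 visits, two per 48-week interval. With a constant 24-week gap, detection is d/24 in every year: 17%, 33% and 50% at 4, 8 and 12 weeks, flat over time.

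**The case against.** - **The table is optional.** SAP 6.5.3 and the synopsis both say that interval analyses may be done, and SAP 6.1 makes the analyses generally descriptive. This stands: the point applies only if the table is produced.
- **A decline is not built in.** A reader might infer from 8/4/2 that hepatic and renal incidence must fall. The documents do not support that. Long-lasting abnormalities are caught at any of these spacings, a rising true rate could offset lost detection, and symptomatic events are recorded from first dose to the final visit whatever the spacing (Protocol 15.2.1). What falls is ascertainment of short, silent episodes.
- **Scheduled tests are not the only route to detection.** Chemistry and urinalysis are also done at relapse, End of Study and premature withdrawal visits, and abnormal results are repeated (Protocol 11.2.1, 14.3.5 to 14.3.7). The Protocol 5.2 list does not say how those AEs were found. This stands and softens the effect by an unknown amount.
- **New starters.** A reader might infer that an early effect in the placebo- and GA-origin groups cannot be told apart from the extra Year 1 testing. It can. Combined Treatment Grouping (SAP 6.2.2, 6.5.1) sets them beside groups continuing BG00012 on the same Year 1 schedule, and that comparison holds testing constant.
- **The size is model-dependent.** A near four-fold fall needs independent results at each test or episodes of about 4 weeks or less.
- **The counts are not exact for everyone.** Subjects who reached Year 4 before Version 3 may have had 12-weekly tests, and 12-month intervals do not match 48-week years.

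None of this removes the confounding, because neither document adjusts for it or warns of it.

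**Conclusion.** The point holds in a limited form. Scheduled chemistry and urinalysis fall from 8 to 4 to 2 per study year. If AE incidence is shown by interval, rows for transient, laboratory-detected hepatic and renal PTs are confounded with testing frequency. At constant risk, the apparent fall from Year 1 to Years 4-8 ranges from none (episodes of 24 weeks or more) through two-fold (12 weeks) and 2.5-fold (8 weeks) to four-fold (4 weeks). This rests on the current schedule, on assumed durations, and on episodes that are silent and not picked up by unscheduled tests. It is a cheap improvement to an optional table. It is no ground for doubting the overall incidence tables, the by-visit laboratory summaries, symptomatic AEs, or comparisons between groups within Year 1.

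**What to change.** In SAP 6.5.3 and 6.5.4:

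1. Base time trends for laboratory-detected hepatic and renal abnormalities on threshold categories, such as the ALT/AST multiples of ULN and the urinalysis grades already in SAP 6.5.4. Use 48-week intervals and only results from the 24-weekly visits common to all years (Weeks 24, 48, 72, ..., 384), and show the number of subjects tested. This also removes the 12-month misalignment and any extra Year 4 or later tests before Version 3.
2. Footnote the AE interval table with the number of scheduled chemistry and urinalysis tests per subject in each interval.
3. State that no trend for laboratory-detected PTs will be drawn from that table alone.

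The cost is one table from existing data and a footnote, with no change to study procedures. The downside is that interim results from Years 1-3 are not used for the trend. These include six of the eight Year 1 tests and every test before Week 24. They remain in the overall incidence, shift and by-visit summaries, where early effects in new starters should be examined. Equal testing also does not correct for changes in who remains on study.

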6.5.4 Analysis of Clinical Laboratory Data

The following clinical laboratory parameters are assessed in the protocol:

- Hematology: hemoglobin, hematocrit, red blood cell count, WBC count (with differential) and platelet count.
- Blood chemistry: sodium, potassium, chloride, total bilirubin, alkaline phosphatase, alanine transaminase/serum glutamate-pyruvate transaminase (ALT/SGPT), aspartate transaminase/serum glutamic-oxaloacetic transaminase (AST/SGOT), lactate dehydrogenase, gamma-glutamyl-transferase (GGT), blood urea nitrogen (BUN), creatinine, bicarbonate, calcium, magnesium, phosphate, uric acid, and glucose.
- Urinalysis: color, specific gravity, pH, protein, glucose, blood, ketones, microscopy, β₂-microglobulin, and microalbumin.
- Urine cytology

Analyses for laboratory data involving baseline value will be based on BG00012 Treatment Baseline (as defined above in Section 6.3.1).

Shift analyses

Laboratory data will be summarized using shift tables where appropriate. Each subject's hematology and blood chemistry values will be flagged as "low", "normal", or "high" relative to the normal ranges of the central laboratory, or as "unknown" if no result is available. Each subject's urinalysis values will be flagged as "positive", "negative", or if no value is available, "unknown".

Shifts from baseline to high/low status for hematology and blood chemistry parameters and shifts from baseline to high/positive status for urinalysis will be presented. Subjects need to have at least one post-baseline evaluation in order to be included in the analysis. In addition, shifts from baseline to the worst post-baseline value will be presented for relevant laboratory tests by treatment group by clinically relevant categories (e.g., \leq ULN, \geq 1 - \leq 3 xULN, \geq 5 - 10 xULN, \geq 10 - 20 x ULN, \geq 20 x ULN, etc.).

For urine cytology tests results, the number and percentage of subjects with an abnormal post-baseline result will be summarized by treatment group.

Summary of laboratory values over time and other analyses

In addition to the shift analyses, summary of actual values, change from baseline values, and percentage change from baseline values will be presented by visit for quantitative laboratory parameters. Graphs showing mean actual values or mean change from baseline values over time may be presented as well.

In addition, summaries of worst post-baseline laboratory values by clinically relevant categories may also be presented for selected parameters of interest by treatment group. The data may also be presented in graphs. For example, for liver function tests (alkaline phosphatase, ALT, AST, GGT and total bilirubin), categories may be defined based on cutoff values relative to the upper limit of normal (e.g., <= ULN, > ULN, >=3 x ULN, >5 x ULN, >10 xULN, and >20 xULN for ALT, AST, and GGT, and <= ULN, > ULN, > 1.5

xULN, and >2 xULN for total bilirubin). For hematology parameters, categories may be defined based on potentially clinically significant cutoffs (e.g., $< 3.0 \times 10^{9}$ /L and >= 16 x 10^9/L for WBC and $< 0.8 \times 10^{9}$ /L, $< 0.5 \times 10^{9}$ /L, and $> 12 \times 10^{9}$ /L for lymphocytes). For qualitative urinalysis parameters, categories may be defined based on the qualitative categories (e.g., normal/negative, trace, 1+, 2+, 3+, etc.).

Worst post-baseline laboratory value summaries will comprise those select safety analyses utilizing the Study 109MS303 Safety Population with Study 109MS303 Treatment Grouping and Study 109MS303 data only, mentioned in the second bullet in Section 6.5.1 above.

6.5.5 Analysis of Vital Signs Data

The analysis of vital signs will focus on the incidence of clinically relevant abnormalities. Analyses for vital signs data involving baseline value will be based on BG00012 Treatment Baseline (as defined above in Section 6.3.1).

The number of subjects evaluated and the number and percentage of subjects with clinically relevant post-baseline abnormalities will be presented by treatment group. The criteria for clinically relevant post-baseline abnormalities (from Table 2 of the protocol) are shown below in Table 6.5.5.1 . Summary statistics for actual values and change from baseline will also be presented.

Table 6.5.5.1 Criteria to Determine Clinically Relevant Abnormalities in Vital Signs

Vital Sign	Criteria for Abnormalities			
Temperature	>38°C and an increase from pre-dosing of at least 1°C			
Pulse	>120 beats per minute post-baseline, or			
	an increase from pre-dosing of more than 20 beats per minute, or			
	<50 beats per minute post-baseline, or			
	a decrease from pre-dosing of more than 20 beats per minute			
Systolic Blood Pressure	>180 mmHg post-baseline, or			
	an increase from pre-dosing of more than 40 mmHg, or			
	<90 mmHg post-baseline, or			
	a decrease from pre-dosing of more than 30 mmHg			
Diastolic Blood Pressure	>105 mmHg post-baseline, or			
	an increase from pre-dosing of more than 30 mmHg, or			
	<50 mmHg post-baseline, or			
	a decrease from pre-dosing of more than 20 mmHg			

Summaries of actual value and change from baseline (based on BG00012 Treatment Baseline) by visit for body weight will also be provided.

[figure not shown]
6.5.6 Analysis of Absolute Lymphocyte Counts

Subjects who temporarily withhold, or permanently discontinue study treatment for any reason and have a lymphocyte count <LLN will continue protocol-required visits and assessments and will also be followed up every 4 weeks for 24 weeks, then every 12 weeks (unless clinically indicated more often or at the Investigator's discretion) until the lymphocyte count is ≥LLN or for up to 48 weeks following drug discontinuation, whichever occurs sooner.

In general, the lymphocyte follow-up analysis may include subjects who have at least one ALC < LLN during the treatment period or at the treatment discontinuation and have at least one ALC value during the lymphocyte follow-up period. Patients who have any post lymphocyte follow-up baseline values may be included in the follow-up analysis. ALCs collected during the lymphocyte follow-up period will be analyzed.

The lymphocyte follow-up period is defined as the time starting from the date of temporary dose interruption or study drug discontinuation. The start date of the lymphocyte follow-up period is defined as the start date of temporary dose interruption or the treatment end date. The last observed value collected on or prior to the date of temporary dose interruption or study drug discontinuation will be the reference point (lymphocyte follow-up baseline). Data that are collected during the lymphocyte follow-up period will be assigned to an appropriate visit by using the mid-point of the two visits windowing scheme. Visits will be mapped every 4 weeks for 24 weeks and then every 12 weeks afterward.

The by-visit summary of actual value change and percent change from BG00012 baseline and the lymphocyte follow-up baseline in ALC during the lymphocyte follow-up period will be presented. The by-visit summary of actual value change and percent change from the study baseline in ALC during the whole study period will also be presented. In addition, graphical display of median (Q1/Q3) of actual value in ALC in the whole study period will be presented; graphical display of median (Q1/Q3) of percent change from BG00012 baseline and lymphocyte follow-up baseline will be presented.

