## 11.3. Monitoring and Management for Subjects with Abnormal Lymphocyte Count

Subjects who have a lymphocyte count  $<500/\text{mm}^3$  at any time should be monitored and managed according to Table 3.

All subjects who complete BG00012 treatment or permanently discontinue BG00012 for any reason other than those specified in Table 3, and who have a lymphocyte count  $<LLN$ , will be monitored every 12 weeks until their lymphocyte count is  $\geq LLN$  OR for 48 weeks after their last dose, whichever is earlier.

CONFIDENTIAL

The information contained herein may not be used, disclosed, or published without the written consent of Biogen MA Inc.

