**Table 3: Lymphocyte Monitoring and Management for Subjects Who Have a Lymphocyte Count  $<500/\text{mm}^3$**

For subjects who have a lymphocyte count  $<500/\text{mm}^3$ , the Investigator should repeat the test as soon as possible. If re-test confirms that the lymphocyte count remains  $<500/\text{mm}^3$ , lymphocyte counts should be monitored every 4 weeks while on BG00012.

If subject has lymphocyte counts  $<500/\text{mm}^3$  for  $\geq 24$  weeks, subject meets the **Temporary Withholding Rule** and BG00012 will be temporarily withheld. If the Temporary Withholding Rule is not met, the subject will be monitored every 12 weeks.

CONFIDENTIAL

The information contained herein may not be used, disclosed, or published without the written consent of Biogen MA Inc.

Lymphocyte Monitoring for Subjects Meeting the Temporary Withholding Rule	Management for Subjects Meeting the Temporary Withholding Rule

The subject will be monitored every 4 weeks for 24 weeks, then every 12 weeks until the lymphocyte count is <math>\geq</math>LLN OR for 96 weeks after their last dose, whichever is earlier. However, if a subject reaches the end of study and their lymphocyte count remains <math><</math>LLN, the subject will be monitored every 12 weeks until the lymphocyte count is <math>\geq</math>LLN OR for 48 weeks after their last dose, whichever is earlier.
	
 
• If lymphocyte count remains <math><500/\text{mm}^3</math> for 24 weeks after temporary withdrawal, BG00012 must be permanently discontinued.
 
• If lymphocyte count is between <math>\geq 500/\text{mm}^3</math> and <math>\leq 800/\text{mm}^3</math>, then BG00012 will continue to be temporarily withheld.
 
• If lymphocyte count recovers to <math>>800/\text{mm}^3</math> (confirmed by 2 tests, at least 4 weeks apart), the physician/patient has the option to restart BG00012. If, upon resumption of BG00012, the lymphocyte count is <math><500/\text{mm}^3</math> on 1 occasion (confirmed by repeat testing), then BG00012 must be permanently discontinued.
 
• Alternative disease-modifying treatmenta may be considered, at the discretion of the treating physician as per standard of care. Subjects treated with alternative disease-modifying treatment will not have the option to restart BG00012.
 

AE = adverse event; CRF = case report form; LLN = lower limit of normal.

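### SAP 6.5.6 states one lymphocyte follow-up schedule where Protocol 11.3 has two, so the pooled by-visit summaries change subject mix at Weeks 8, 20 and one of 12/16

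*SAP*

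**What the plan says.** SAP 6.5.6 covers subjects who temporarily withhold or permanently discontinue for any reason with a count below LLN. It says they "will also be followed up every 4 weeks for 24 weeks, then every 12 weeks" until the count is back at LLN "or for up to 48 weeks following drug discontinuation, whichever occurs sooner". Data are assigned to visits "by using the mid-point of the two visits windowing scheme", and "Visits will be mapped every 4 weeks for 24 weeks and then every 12 weeks afterward". By-visit summaries of change and percent change, and median (Q1/Q3) plots, are planned on that grid. No split by schedule or severity is specified.

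Protocol 11.3 has two arrangements.

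- **Temporary Withholding Rule subjects** (below 500/mm³ for at least 24 weeks). Table 3 says: "The subject will be monitored every 4 weeks for 24 weeks, then every 12 weeks until the lymphocyte count is" at LLN "OR for 96 weeks after their last dose, whichever is earlier". If such a subject reaches end of study still below LLN, testing is 12-weekly for up to 48 weeks after last dose.
- **Everyone else below LLN** who completes treatment, or who "permanently discontinue BG00012 for any reason other than those specified in Table 3". They "will be monitored every 12 weeks until their lymphocyte count is" at LLN, or for 48 weeks after last dose.

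Elsewhere the SAP agrees with the protocol. Section 2.2 says completers and permanent stoppers below LLN were followed under Protocol 11.3. Section 3.5 gives hematology at 4 or 12 weeks by reference to Protocol Table 3. Section 3.6 shows lymphocyte follow-up to 96 weeks. Section 6.5.8, on deviations from the protocol, does not mention the difference.

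**The concern.** Under the current protocol, how often a subject is tested after stopping depends on how low the count was and for how long. If everyone is placed on one 4-weekly grid, membership of a column depends on severity. This is separate from subjects leaving follow-up once they recover, which thins all later columns. Here the mix can alternate between adjacent columns.

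The primary objective is long-term safety. The amendment log ties prolonged severe lymphopenia to PML, and explains the longer follow-up by evidence that recovery may take more than 6 months. The post-treatment count curve is the output meant to show that recovery. If its median shifts because different people are in the column, a reader could take the shift for recovery or relapse of the count. The 48-week limit in 6.5.6 also leaves unclear how Week 48 to 96 data are to be presented.

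**Working it through.** The plan states no figure on this point. The check maps each protocol schedule onto the SAP columns.

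**Inputs.** The grid is Weeks 4, 8, 12, 16, 20, 24, 36 and 48 (SAP 6.5.6). Windows end at midpoints, with the midpoint in the later window (SAP 6.3.8; 6.5.6 does not say which side). Taking the stop date as Day 1, Week w is Day 7w + 1. The Week 8 window, for example, starts at (29 + 57)/2 = Day 43. All subjects have a blood count at the Premature Study Treatment Withdrawal Visit, within 4 weeks of last dose, or at the End of Study Visit (Protocol 7.2.3, 14.3.5, 14.3.7). The protocol does not say whether the 12-weekly tests run from last dose or from that visit, so both are shown.

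| Column | Window (days) | 4-weekly schedule | 12-weekly from last dose | 12-weekly from a visit at Week 2 to 4 |
|---|---|---|---|---|
| 4 | 2–42 | yes | withdrawal/End of Study draw | withdrawal/End of Study draw |
| 8 | 43–70 | yes | none | none |
| 12 | 71–98 | yes | Day 85 | none |
| 16 | 99–126 | yes | none | Days 99–113 |
| 20 | 127–154 | yes | none | none |
| 24 | 155–210 | yes | Day 169 | Days 183–197 |
| 36 | 211–294 | yes | Day 253 | Days 267–281 |
| 48 | 295 on | yes | Day 337 | none within 48 weeks |

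A ±7-day shift does not change the last-dose column (Day 78–92 stays in Week 12, Day 162–176 in Week 24). So, of the six columns to Week 24, a 12-weekly subject has a scheduled draw in three and none in the other three: Week 8, Week 20 and one of 12/16. Under the current protocol, scheduled follow-up tests after Week 48 come only from the withholding-rule group.

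**Who else fills the in-between columns.**

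- Subjects who stopped under earlier protocol versions. The amendment log shows these were followed 4-weekly for up to 24 weeks at any count below LLN.
- Subjects interrupted for AST/ALT or for flushing/GI symptoms. Those withheld for laboratory values stay on the Section 4 calendar (Protocol 11.2.1), which is anchored to the Baseline Visit (Protocol 7.2.2), so their draws can fall in any column.
- Draws at unscheduled relapse visits or at the investigator's discretion.

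**Size of the withholding-rule group.** The only figure is in the amendment log: 2% of subjects in the BG00012 studies had counts below 0.5 × 10⁹/L for at least six months. 0.02 × 1738 randomised = 34.8. 0.02 × 1000 (approximate number ongoing, quoted in the amendment that introduced 12-weekly follow-up) = 20.

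**Are 12-weekly subjects the majority?** Let p be the share below LLN at stopping, which the documents do not give, and assume 2% meet the rule. The 12-weekly share is (p − 0.02)/p: 33% at p = 3%, 50% at 4%, 80% at 10%, 93% at 30%.

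**Share of rule-meeters in the in-between columns.** Let x subjects have stopped under the earlier 4-weekly rule (not given; about 1738 − 1000 = 738 were no longer ongoing). Ignoring incidental draws, the share is (20 + 0.02x)/(20 + px).

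| x | p = 10% | p = 20% | p = 30% |
|---|---|---|---|
| 0 | 100% | 100% | 100% |
| 50 | 84% | 70% | 60% |
| 100 | 73% | 55% | 44% |
| 200 | 60% | 40% | 30% |
| 400 | 47% | 28% | 20% |

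The mix differs from neighbouring columns throughout, but its make-up depends on x and p.

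**The case against.** The case for leaving the plan alone has several parts.

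- The wrong description is in one paragraph. The rest of the SAP defers to Protocol 11.3, and 6.5.6 does not govern data collection. The mapping sentence itself matches Table 3, sets no 48-week cap and suits data collected under earlier versions. This stands: the fault is the single schedule described for everyone, and the pooling that goes with it.
- The analysis is descriptive. SAP Section 6 reports the number of subjects with data and warns about sparse later timepoints. This stands in part. N per column would reveal a change in mix but would not remove it, and the warning concerns late timepoints, not alternation within the first 24 weeks.
- A reader might infer that the 4-weekly columns mainly describe the most lymphopenic subjects. The documents do not support that. Week 4 is filled by everyone with a withdrawal or End of Study draw, Week 24 and one of Weeks 12/16 by the 12-weekly group, and the in-between columns also hold earlier-version and incidental draws.
- It is also tempting to say that most subjects below LLN are tested 12-weekly, or that the in-between columns rest on at most 35 people. No count below LLN at stopping is given, and the 2% comes from pooled studies at an earlier date, so it is not an upper bound here.
- The reference in 6.5.6 to continuing protocol-required visits is not an error. Such visits exist both for withheld subjects and for permanent stoppers.

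**Conclusion.** The point holds in limited form. SAP 6.5.6 conflicts with Protocol 11.3 and with SAP 2.2, 3.5 and 3.6 on who is tested 4-weekly, on completers (whom its schedule sentence omits) and on the 48- versus 96-week limit. The passages must be reconciled. As a consequence, the pooled by-visit medians and percent changes can move with composition at Weeks 8, 20 and one of 12/16. Beyond Week 48, current-protocol scheduled data describe the withholding-rule group alone.

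The size of the shift cannot be computed from the documents. The figures of about 20 or 35 subjects are illustrations that assume the 2% carries over to this cohort. The column mapping assumes the midpoint rule of SAP 6.3.8 and a count from the stop date. To call the recovery curve uninterpretable would go too far: Weeks 24 and 36 are shared by both schedules, and Week 48 too when tests run from last dose.

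**What to change.** Reconcile the 6.5.6 text with Protocol 11.3 so that it describes the schedules under which the data were collected, including completers, the 96-week limit and the end-of-study provision. This concerns the SAP's description and tables, not how subjects are followed.

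Present follow-up counts by follow-up schedule:

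- (a) Temporary Withholding Rule subjects on the 4-weekly then 12-weekly grid to Week 96, noting those moved to 12-weekly testing at end of study.
- (b) Other subjects below LLN at stopping or completion, on 12-weekly windows (Weeks 12, 24, 36, 48).
- (c) Subjects followed 4-weekly under earlier protocol versions, shown separately on their own grid. Collapsing them to 12-weekly windows throughout would discard early-recovery data.

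Show N in every column and under every plot. Restrict any pooled line to the common 12-weekly timepoints, with windows wide enough to catch tests counted from either anchor.

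The cost is a wording change and one extra table split on existing data. Some groups, probably (a), will be small.
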